#### Potential confounders to be evaluated:

 Baseline: age, gender, race, ethnicity, region, marital status, risk of HIV transmission, payer type, CD4 cell count, viral load, prior regimen, years since HIV diagnosis and ART initiation, weight, BMI, co-infections, comorbidities, concomitant medications

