#### 6.3.3. Confounders and effect modifiers

#### 6.3.3.1. Confounders

The following baseline characteristics will be evaluated as potential confounders:

- Demographic characteristics at index
  - Age (years, as well as categorized as 18-50, 50-64, 65+)
  - Sex (male, female)
  - Race (African American/Black, Asian, White, other race, unknown)
  - Ethnicity (Hispanic, non-Hispanic)
  - Marital status (Single, married/domestic partner, widowed, separated/divorced, unknown)
  - Geographic region (Northeast, Midwest, South, West, US Territories)
  - Risk of HIV transmission (MSM, PWID, Heterosexual, Vertical, Other)
  - Payer type (Medicaid, Medicare, Commercial insurance, AIDS Drug Assistance Programs (ADAP)/Ryan White, Cash)
- Clinical characteristics at index
  - Years since HIV diagnosis
  - Years since ART initiation
  - AIDS diagnosis at baseline

- Years since first OPERA visit
- Veterans Aging Cohort Study (VACS) Mortality Index score
- Weight (kg)
- $\circ \quad BMI (<30 \text{ vs.} \ge 30 \text{ kg/m}^2)$
- Co-infections
  - Hepatitis B co-infection
  - Hepatitis C co-infection
  - Syphilis infection (ever)
- o Comorbidities
  - Autoimmune disease
  - Cardiovascular disease
  - Invasive cancer
  - Endocrine disorder
  - Mental health disorder
  - Liver disease
  - Bone disorder
  - Peripheral neuropathy
  - Renal disease
  - Hypertension
  - Substance abuse
  - Any of the above
- Concomitant Medications
  - Anticonvulsants
    - Carbamazepine
    - Oxcarbazepine
    - Phenobarbital
    - Phenytoin
  - Antimycobacterials
    - Rifampin
    - Rifapentine
    - Rifabutin
  - Glucocorticoids
    - Dexamethasone
  - Macrolide or ketolide antibiotics
    - Azithromycin
    - Clarithromycin
    - Erythromycin
  - Narcotic analgesic
    - Methadone
- ART regimens prior to CAB+RPV LA
  - Number of core agents experienced
  - o Number of ARV classes experienced
  - Duration of last ARV regimen
  - o Prior core agent class
- Baseline virologic characteristics
  - o HIV viral load
    - Test result available (yes/no)
    - Continuous (copies/mL and log10 copies/mL)

- Categorical
  - o <50 copies/mL
  - $\circ$   $\geq$ 50 to  $\leq$ 200 copies/mL
  - $\circ \geq 200 \text{ to } < 1,000 \text{ copies/mL}$
  - $\circ \ge 1,000 \text{ to} < 10,000 \text{ copies/mL}$
  - $\circ \ge 10,000 \text{ to } < 100,000 \text{ copies/mL}$
  - $0 \ge 100,000 \text{ copies/mL}$
  - Missing
- Baseline immunologic characteristics
  - o CD4 cell count

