# 6.7. \*Data analysis

# 6.7.1. Primary Analysis

## 6.7.1.1. Main Analytical approach

Baseline characteristics and outcomes will be described using counts and absolute and relative frequencies for categorical variables and medians with interquartile ranges (IQR) for continuous variables. For outcomes assessed at any point during follow-up, incidence rates will be estimated using unadjusted Poisson regression, accounting for person-time since index (i.e., first CAB+RPV LA injection).

Analyses will be stratified by viral load (<50 copies/mL vs. ≥50 copies/mL), BMI (<30 kg/m² vs. ≥30 kg/m²), age (18-50, 50-64, ≥65 years), race/ethnicity (non-Hispanic Black, Hispanic, non-Hispanic White), and sex/race (non-Hispanic Black men, Hispanic men, Black women) strata at first CAB+RPV LA injections as sample size allows to assess characteristics, adherence, persistence, discontinuation and virologic effectiveness. Other demographic and clinical variables may also be considered for stratification, if relevant.

Factors including age, sex, race, geographic region, BMI, IDU, CD4 count, any comorbidities associated with confirmed virologic failure will be assessed using multiple logistic regression.

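### The factors named for the confirmed virologic failure model leave out baseline viral load, and the protocol does not say whether the model is pooled over, or fitted within, viral load strata

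*Protocol*

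**What the plan says.** The only multivariable model in the protocol is in 6.7.1.1 and answers primary objective 4: "Factors including age, sex, race, geographic region, BMI, IDU, CD4 count, any comorbidities associated with confirmed virologic failure will be assessed using multiple logistic regression". The corresponding synopsis sentence names no covariates.

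Two other places list potential confounders, and both include viral load and ethnicity:

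- The synopsis gives "age, gender, race, ethnicity, region, marital status, risk of HIV transmission, payer type, CD4 cell count, viral load, prior regimen" and continues from there.
- Section 6.3.3.1 opens with "The following baseline characteristics will be evaluated as potential confounders". Its list includes "Ethnicity (Hispanic, non-Hispanic") and, under "Baseline virologic characteristics", HIV viral load in continuous and categorical form.

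In 6.7.1.1, the paragraph before the model sentence says "Analyses will be stratified by viral load (<50 copies/mL vs. ≥50 copies/mL") and by other subgroups, "as sample size allows to assess characteristics, adherence, persistence, discontinuation and virologic effectiveness".

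Section 6.3.2.6 gives CVF separate definitions by baseline viral load. A suppressed starter can meet it from the start of follow-up. A viremic starter must first reach <50 copies/mL. Objective 4 in Section 5 covers everyone receiving CAB+RPV LA. Section 6.7.1.2 plans no sensitivity analyses.

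**The concern.** The protocol chose to name covariates for this model, and the named set does not match its own confounder lists. The gap for viral load matters most, because baseline viral load also decides which CVF definition applies to a person.

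If the model is pooled without viral load, a factor that is merely more common among viremic starters picks up part of the difference in CVF between viremic and suppressed starters. CD4 count is the obvious candidate. A reader of the Year 3, 4 or 5 results could then take as a predictor of failure something that only marks how people entered the cohort. The contrast that would explain it, starting viremic or not, would have no estimate in the model.

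Ethnicity is a lesser matter of consistency. It is in both confounder lists and is used with race in the subgroup definitions, but the model sentence names race only.

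**Working it through.** **The plan's own figures.** The counts in 6.5 add up: 1,578 + 229 + 36 = 1,843. All 44 interval widths in Table 1 reproduce with 2 × 1.96 × √(p(1−p)/n). At p = 0.5 they are 0.0457 (n = 1,843), 0.0493 (1,578), 0.1681 (136) and 0.2032 (93), against the stated 0.05, 0.05, 0.17 and 0.20. The protocol gives no precision or event count for the logistic model.

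**Share starting viremic.** 229 / (1,578 + 229) = 229 / 1,807 = 12.7%.

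**Inputs for the illustration.** Only the 12.7% comes from the protocol. The rest are assumptions:

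- CD4 <200 in 3% to 5% of suppressed and 15% to 25% of viremic starters
- CVF risk of 1.2% in suppressed starters
- odds ratio for CVF, viremic versus suppressed, of 2 to 5, and 0.5 as a check in the other direction
- no effect of CD4 within either stratum (true odds ratio 1.0)

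**One case in full** (CD4 <200 in 5% and 25%; viremia odds ratio 3):

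1. CVF risk in viremic starters: odds = 3 × 0.012/0.988 = 0.03644; risk = 0.03644/1.03644 = 3.52%.
2. Viremic share among those with CD4 <200: 0.127×0.25 / (0.127×0.25 + 0.873×0.05) = 0.0317/0.0753 = 42.0%.
3. Viremic share among those with CD4 ≥200: 0.127×0.75 / (0.127×0.75 + 0.873×0.95) = 10.3%.
4. CVF risk with CD4 <200: 0.420×3.52% + 0.580×1.2% = 2.17%. With CD4 ≥200: 0.103×3.52% + 0.897×1.2% = 1.44%.
5. Crude odds ratio: (0.0217/0.9783) / (0.0144/0.9856) = about 1.52, where the true value is 1.0.

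**Range over the assumed CD4 prevalences:**

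| Assumed viremia odds ratio | Crude odds ratio of a null CD4 factor |
|---|---|
| 0.5 | 0.76 to 0.90 |
| 2 | 1.17 to 1.40 |
| 3 | 1.30 to 1.74 |
| 5 | 1.51 to 2.27 |

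If the factor is unrelated to viremia, the odds ratio is 1.00 whatever the viremia odds ratio. With viral load in the model, or with the model fitted within strata, it is 1.00 by construction.

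**Could the model be fitted in each stratum?** At an assumed CVF proportion of 1% to 5%, 229 viremic starters give 229×0.01 = 2.3 to 229×0.05 = 11.5 events. That is too few for eight or more factors at the two-year numbers. The cohort is expected to grow, but the protocol gives no projected size.

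**The case against.** The case on the other side has four parts.

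*The list is open.* The sentence says that the factors include the eight, so viral load is not excluded, and 6.3.3.1 commits to evaluating it as a potential confounder. A full covariate list is also commonly left to the statistical analysis plan. This stands against any claim that viral load will be absent from the model. It does not remove the point that the protocol names region and BMI but not the variable on which its own outcome definition depends.

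*Stratification may cover it.* The preceding paragraph stratifies by viral load for virologic effectiveness, and CVF is defined under that heading, so models within strata are a fair reading. Against that, stratification is conditional on sample size, the model stands in its own paragraph without mention of strata, objective 4 is separate from the virologic effectiveness objective, and a viremic-only model would be very thin. The text leaves the matter open.

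*The direction is unknown.* Viremic starters must suppress before they can count as CVF, and those who never suppress are described as non-response. Their odds of CVF could be below those of suppressed starters. This stands, and the odds ratio of 0.5 is shown for that reason.

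*The sizes are crude and rest on assumptions.* They ignore the other seven named factors, and most inputs are not in the protocol. This also stands.

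A reader might infer that the adjusted odds ratios for CD4 count, race and the rest will carry the effect of starting viremic, and in an upward direction. The protocol supports neither: the distortion needs a pooled model without viral load, and its sign is open. Nor is any numerical consequence shown for leaving out ethnicity.

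**Conclusion.** The point holds conditionally. The named covariates do not match the protocol's confounder lists, and the protocol does not fix whether the CVF model is pooled or stratified by baseline viral load.

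If it is pooled over all initiators, as objective 4 is worded, and uses only the named factors, odds ratios for factors related to starting viremic can be confounded in either direction. On the assumed inputs, a null CD4 factor would show a crude odds ratio of about 1.2 to 2.3 for viremia odds ratios of 2 to 5, and 0.76 to 0.90 for 0.5. These figures show that the effect could be material. They do not predict what the study will report.

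Because this is a primary objective and the remedy costs little, the sentence should be amended. The ethnicity mismatch is a consistency point only.

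**What to change.** In Protocol 6.7.1.1, do one of the following:

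- make baseline viral load (<50 vs ≥50 copies/mL) a required term in a CVF model pooled over all initiators; or
- state that the model is fitted in those suppressed at initiation, with CVF in the viremic stratum described separately.

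The first keeps objective 4 as worded, but the outcome still combines two definitions, and the report should say so. The second gives one outcome definition but narrows the objective to suppressed starters.

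Under either option, state how people without a baseline viral load are handled (36 in 6.5), since 6.3.2.6 gives them no CVF definition. Add ethnicity to race, in line with the synopsis and 6.3.3.1. Keep the Asian, other and unknown race categories: the three-level race/ethnicity subgroup variable has no place for them and should not simply replace race. Then reconcile the synopsis and 6.3.3.1 lists with the model's list.

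**Cost.** A few sentences, with no new data, since both variables are already collected. The model takes one or two extra degrees of freedom for viral load and a few for ethnicity. That is not entirely free. On the assumed 1.2% risk and viremia odds ratio of 3, the two-year numbers give about 1,578×0.012 = 19 plus 229×0.0352 = 8, or 27 events, and race and region at five levels each already take 4 + 4 = 8 degrees of freedom. The expected growth of the cohort eases this.

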#### **Primary Objectives:**

- 1. To describe baseline demographics, clinical characteristics and patterns of use among PWH receiving CAB+RPV LA at Year 3, Year 4, and Year 5 of availability
- 2. To assess the persistence, adherence and discontinuation among PWH receiving CAB+RPV LA at Year 3, Year 4, and Year 5 of availability
- 3. To assess virologic effectiveness among PWH receiving CAB+RPV LA at Year 3, Year 4, and Year 5 of availability
- 4. To assess factors associated with confirmed virologic failure among PWH receiving CAB+RPV LA regimen at Year 3, Year 4, and Year 5 of availability

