## **Study Period:**

- o Year 3:
  - Period of eligibility: 21JAN2021-31DEC2023
  - Period of observation: 21JAN2021-29FEB2024
- O Year 4:
  - Period of eligibility: 21JAN2021-31DEC2024
  - Period of observation: 21JAN2021-28FEB2025
- o Year 5:
  - Period of eligibility: 21JAN2021-31DEC2025
  - Period of observation: 21JAN2021-28FEB2026

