#### **Censoring criteria:**

- Discontinuation of regimen of interest
- Death
- Loss to follow-up (12 months after last clinical contact)
- Study end (end of observation period: 29FEB2024, 28FEB2025, 28FEB2026)

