## 6.3.2.6. Virologic effectiveness

Among suppressed (VL< 50 copies/mL) at initiation:

Maintaining virologic suppression: Among PWH who were suppressed (VL <50 copies/mL) at baseline, the number and proportion who remain suppressed (VL <50 copies/mL) throughout all of follow-up will be reported, as well as the number and proportion who are suppressed (VL <50 copies/mL) at last follow-up. Proportion of individuals with VL <50 copies/mL during the first 6 months, and at 6, 12, 24, 36, 48, and 60 months following initiation of CAB+RPV LA regimen will be described.

Confirmed virologic failure: Confirmed virologic failure will be defined as 2 consecutive follow-up VLs ≥200 copies/mL OR 1 follow-up VL ≥200 copies/mL + discontinuation within 4 months of VL ≥200 copies/mL. The number and proportion of PWH with confirmed virologic failure will be reported as well as the time to virologic failure (months). Proportion of individuals with confirmed virologic failure (CVF) during the first 6 months, and at 6, 12, 24, 36, 48 and 60 months following initiation of CAB+RPV LA regimen will be described.

Among viremic ( $VL \ge 50$  copies/mL) at initiation:

Achieving virologic suppression: Among PWH who were viremic ( $VL \ge 50$  copies/mL) at baseline, the number and proportion who achieve a VL < 50 copies/mL at any point during follow-up will be reported, as well as the number and proportion who achieve a VL < 50 copies/mL at last follow-up. Proportion of individuals with VL < 50 copies/mL during the first 6 months, and at 6, 12, 24, 36, 48 and 60 months following initiation of CAB+RPV LA regimen will be described.

Non-response: VL ≥50 copies/mL after 6 and 12 months following initiation of CAB+RPV LA regimen and also no VL of <50 copies/mL during follow up will be described.

Confirmed virologic failure defined as:

- Suppressed to <50 copies/mL followed by either 2 VLs ≥200 copies/mL or
  1 VL ≥200 copies/mL and discontinuation within 4 months for every other month
  regimen; and discontinuation within 2 months for monthly regimen. Proportion of
  individuals with confirmed virologic failure (CVF) during the first 6 months, and at
  6, 12, 24, 36, 48 and 60 months following initiation of CAB+RPV LA regimen will
  be described.

- FDA's ask: Suppressed to <50 copies/mL followed by either 2 VLs ≥400 copies/mL

Protocol Final ViiV Healthcare 216990 - Amendment 2

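### Primary objective 4 (factors associated with CVF) uses ever/never logistic regression although potential follow-up runs from about 2 to 61 months, so odds ratios mix failure risk with time at risk

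*Protocol*

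**What the plan says.** Primary objective 4 (Protocol section 5, repeated in the synopsis) is "To assess factors associated with confirmed virologic failure among PWH receiving CAB+RPV LA regimen", at Years 3, 4 and 5. For it, section 6.7.1.1 names age, sex, race, region, BMI, IDU, CD4 count and comorbidity, and closes with "any comorbidities associated with confirmed virologic failure will be assessed using multiple logistic regression". The synopsis also names logistic regression. Neither place gives a horizon, a minimum follow-up, a time term or an analysis set. Section 6.7.1.2 plans no sensitivity analyses.

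The windows in section 6.2 are, for Year 5, "Period of eligibility: 21JAN2021-31DEC2025" and "Period of observation: 21JAN2021-28FEB2026". For Year 3 the last eligible start is 31DEC2023, with "Period of observation: 21JAN2021-29FEB2024". The censoring criteria add "Discontinuation of regimen of interest", death and loss to follow-up.

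Section 6.3.2.6 defines CVF differently by baseline viral load. For starters with VL <50 copies/mL it is two consecutive VLs ≥200, or one VL ≥200 plus discontinuation within 4 months. For viremic starters it begins "Suppressed to <50 copies/mL followed by either 2 VLs", so a prior VL <50 is required; non-response is described as a separate outcome.

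For outcomes assessed at any point in follow-up, 6.7.1.1 also plans incidence rates from unadjusted Poisson regression, "accounting for person-time since index (i.e., first CAB+RPV LA injection").

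**The concern.** A yes/no model gives the same non-failure code to a person followed for two months and to a person followed for five years without failure. If a factor is commoner among late starters, or among people who stop the regimen early, those people have less time in which to fail, and the factor looks protective for that reason alone. A factor commoner among early starters looks harmful. Nothing in the stated model corrects this, and with no sensitivity analysis nothing would expose it.

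The CVF definition for viremic starters raises a second issue. A person who stays viremic throughout cannot meet it, so if viremic and suppressed starters share one model, that person is coded the same as a success. Within the viremic stratum, person-time from first injection also includes time during which CVF is impossible.

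At stake is the protocol's only adjusted analysis with a named model, and it serves a primary objective.

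**Working it through.** **Inputs from the protocol.** The eligibility and observation windows and censoring criteria (6.2); the CVF definitions (6.3.2.6); and the counts at first injection in 6.5: 1,578 with VL <50, 229 with VL ≥50 and 36 without a VL. These add to the stated 1,843, and 1,578 + 229 = 1,807 have a VL.

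**Inputs that are assumed.** The protocol gives no CVF rate, discontinuation rate, share never suppressing or time to suppression. Values for these are marked as assumptions below.

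**1. Potential follow-up, before other censoring** (end of observation minus last and first possible index date; 30.4375 days per month)

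| Analysis | Shortest | Longest |
|---|---|---|
| Year 3 | 60 days (2.0 months) | 1,134 days (37.3 months) |
| Year 4 | 59 days (1.9 months) | 1,499 days (49.2 months) |
| Year 5 | 59 days (1.9 months) | 1,864 days (61.2 months) |

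At Year 5 the ratio is 1,864/59 = 31.6.

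**2. Follow-up alone moves the odds ratio.** With constant CVF hazard h, the probability of ever failing in time T is 1 − exp(−hT). Take h = 1 per 100 person-years in both groups (assumed), so the true hazard ratio is 1.0. With 36 months at risk the probability is 0.0296; with 24 months it is 0.0198. The odds ratio is (0.0296/0.9704)/(0.0198/0.9802) = 1.51.

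**3. A factor that drifts over calendar time (Year 5 window).** Let u run from 0 to 1 across the entry period, with uniform entry.
- Potential follow-up: T(u) = 1,864 − 1,805u days.
- Prevalence of the factor: 0.20 + 0.40u (assumed).
- Discontinuation: d per year, the same in both groups (assumed).
- Probability of CVF: h/(h+d) × [1 − exp(−(h+d)T)], with h = 0.01 per year and hazard ratio 1.0.

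With d = 0.20, averaging over entry gives 1.654% with the factor and 2.060% without it. The odds ratio is (0.01654/0.98346)/(0.02060/0.97940) = 0.80. Mean time at risk is 19.9 versus 24.7 months, and the person-time rate ratio is 1.00. Varying d from 0 to 0.30 moves the odds ratio from 0.76 to 0.82.

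**4. Balanced follow-up.** With the same entry pattern and d = 0.10 in both groups, and h between 1 and 5 per 100 person-years, a true hazard ratio of 1 gives an odds ratio of 1.00, and a true hazard ratio of 2 gives 2.01 to 2.06. The distortion needs a link between the factor and time at risk.

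**5. Viremic starters, if pooled.** Assume equal hazards of 2 per 100 person-years once suppressed, 24 months of follow-up and 4 months to suppression. If 10% to 30% never suppress, the ever-CVF odds ratio for viremic versus suppressed starters is 0.74 down to 0.58, with no difference in hazard once at risk.

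**6. CVF rate in the viremic stratum.** Let q be the share never suppressing, s the time to suppression and T the follow-up. The rate per person-time since index, relative to the rate per person-time actually at risk, is (1 − q)(T − s)/T. With T = 2 years (all values assumed):
- q = 0.10, s = 0.25 years: 0.90 × 1.75/2 = 0.79, understated by 21%.
- q = 0.30, s = 0.50 years: 0.70 × 1.50/2 = 0.525, understated by 48%.

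Over a wider range (q from 0 to 0.30, s from 2 to 6 months, T of 12 or 24 months) the ratio runs from 0.92 to 0.35. Viremic starters are 229/1,807 = 12.7% of those with a VL. With equal mean follow-up in the two strata, the pooled denominator therefore changes by only 0.127 × 0.08 = 1% to 0.127 × 0.65 = 8%.

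**The case against.** **The rates already use person-time.** This stands. A reader might infer that CVF rates in general are distorted by unequal follow-up. They are not: the Poisson analysis divides by time, so rates in suppressed starters are unaffected. Only the viremic-stratum rate is in question. Even there, a rate since initiation answers a different question from a rate since suppression; it misleads chiefly when set beside the rate in suppressed starters.

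**The protocol does not say that the logistic model pools the viral-load strata.** This stands too. CVF is defined by stratum and virologic effectiveness is stratified by viral load, so a model within strata fits the text. The analysis set may be settled in the SAP. The point about never-suppressed people is therefore conditional on pooling. The choice of logistic regression is not left open in this way.

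**Discontinuation is not pure censoring.** One VL ≥200 followed by discontinuation within the window is itself a CVF. A reader might infer that a factor which only raises discontinuation must look strongly protective at a true hazard ratio of 1.0. The definition rules that out, because such a factor also raises CVF. For that reason the illustration keeps discontinuation equal in both groups and lets only the start date differ.

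**Few events per parameter.** A reader might take the small event proportions in Table 1 as expected CVF risks and conclude that the model is overfitted. The table is a generic precision grid up to 0.9, its sample sizes are two-year counts expected to grow, and the coding of the factors is not fixed. The protocol does not support that argument.

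**The analyses are called descriptive (6.9.1), and fixed CVF time points exist (6.3.2.6).** No decision rule rests on the odds ratio, but an association reported for a primary objective should still measure failure risk. The 6- to 60-month proportions are descriptive and not tied to the model. They do offer a simpler repair.

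**Conclusion.** The concern holds for the odds ratios. Section 6.7.1.1 fixes a model that ignores time at risk, in a cohort whose potential follow-up varies 19-fold at Year 3 (1,134/60) and about 32-fold at Year 5. The follow-up range comes directly from the protocol's dates. The size of the bias does not: an odds ratio of about 0.8 for a null factor rests on the assumed CVF rate, uniform entry and a prevalence rising from 20% to 60%. With balanced follow-up and uncommon CVF, the bias largely disappears.

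The viremic issue holds in narrower form. It affects the factor model only if the strata are pooled, and it affects rates only within the viremic stratum: 21% to 48% too low under the stated assumptions, and about 1% to 8% in the pooled rate.

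Because this is a primary objective with no sensitivity analysis behind it, the model should be changed before the remaining analyses are reported.

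**What to change.** In 6.7.1.1 and the synopsis:

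- **Model.** Replace multiple logistic regression by a Cox model, or by Poisson regression with a log person-time offset, adjusted for calendar time of index. The person-time is already being built for the incidence rates.
- **Event date.** Date the failure at the qualifying VL, so that a VL ≥200 followed by discontinuation within the window counts as an event and is not lost to censoring at discontinuation.
- **Analysis set.** Fit the main model in people with VL <50 copies/mL at index. Analyse viremic starters separately, at risk from their first VL <50, and show non-response beside CVF.
- **Alternative.** If odds ratios are wanted, use logistic regression at one of the horizons already listed in 6.3.2.6, among people with adequate follow-up for that horizon. This excludes late starters.

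Cost: protocol and SAP wording and minor programming. Hazard or rate ratios replace odds ratios, so earlier-year results need a re-run for comparability. The main model then covers suppressed starters only, which is narrower than the population named in objective 4 and should be stated.
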